4.2.1.3 Model Assessment

Explained variation will be examined by Cox and Snell's R^2 . The updated model(s) will be internally assessed according to discrimination and calibration. Calibration refers to how closely the probability of the event predicted by the model agrees with the observed probability. It will be assessed graphically [60] – if predicted and observed probabilities agree over the whole range of probabilities, the plots will show a 45° line. Discrimination refers to the ability of the prognostic model to differentiate between those who experience the event during the study and those who do not. The discriminative ability of the model will be measured with the c-index which is equivalent to the area under the ROC curve [61]. The c-index is measured on a scale ranging from 0.5 (no better than chance) to 1 (perfect prognostic) [62].

4.2.2 Developing a novel prognostic model

As described above, a recent systematic review identified several prognostic models and many prognostic factors described as associated with transition to psychosis in patients with ARMS. The authors of that review highlighted the poor methodological quality of the included studies and specifically stated that future studies should more strictly adhere to current checklists and guidelines on clinical prognostic models, such as the recently published TRIPOD statement [63]. Other recommendations included using an appropriate sample size, undertaking internal and external validation, and reporting model performance.

Given the poor quality of existing prognostic models and factors within this field [41], it is likely that model updating is still going to lead to a prognostic model which demonstrates poor discrimination in particular on internal validation. Even though the IPD will help to avoid some issues such as poor reporting of missing data and categorisation of continuous prognostic factors, model updating may not be sufficient to produce a well-performing prognostic model. In that case, we will develop a

novel prognostic model using the IPD from Phase 1, which will not suffer from the specified methodological flaws so frequently seen within prognosis research as outlined above.

4.2.2.1 Data

Given that the purpose of our model is to stratify patients at risk of transitioning to psychosis within the NHS, we will only use IPD from Phase 1 from prognostic models developed within the United Kingdom, or from countries with an equivalent healthcare system. Use of the IPD will enable standard analysis methods to be used across the IPD datasets and consistent predictor and outcome definitions [26]. The transportability of the novel model will be assessed by considering the discrimination and calibration of our model within the other IPD, obtained from outside of the UK.

We will make ensure that our dataset reports at least 10 transition events per variable (EPV)[64]. This may restrict the number of prognostic factors we can consider for inclusion in the model, but we will assess this once we have produced our list of candidate predictors and are aware of the relevant data from Phase 1.

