Identifying studies - **electronic searches:** Titles, abstracts and keywords will be searched in the publication databases using search terms adapted from previous systematic reviews and meta-analyses of this research area [33, 38-41]:

['psychosis'] AND ["clinically at high risk' OR 'clinically at risk' OR 'clinical high risk' OR 'ultra-high risk' OR prodrom* OR 'at risk mental state' OR 'risk of psychosis' OR " OR 'ARMS' OR 'prodromal psychosis']

Study selection process: Titles and abstracts will be screened for relevance, and full-text reports will be assessed for eligibility against the abovementioned study selection criteria. When required, additional information to ascertain eligibility will be requested from study authors. Discrepancies in selection decisions will be discussed, and arbitration by another member of the research team sought to resolve such discrepancies.

IPD collection process: IPD will be collected from principal investigators and data custodians of past and on-going ARMS prospective studies identified using the search strategy described above. We have already set up a collaborative network of active researchers in this area to support the retrieval of relevant IPD and have approached the principal investigators/data custodians of several of the most relevant ARMS prospective studies internationally. We will continue to expand the collaborative network by sending invitation emails to all relevant researchers and invite them to share available IPD for this IPD meta-analysis.

Prognostic factors: This evidence synthesis will focus on prognostic factors that can be feasibly assessed in routine clinical practice in the NHS. Our data requests will consider a range of variables that have been examined in previous primary research aimed at identifying predictors of psychosis transition (for a review see [41]), including:

- 1) Socio-demographic characteristics (e.g. age, gender, ethnicity, SES, education);
- 2) Clinical characteristics, including baseline measures of specific ARMS risk criteria, general/social/occupational functioning, general psychopathology, positive symptoms, negative symptoms, disorganisation, anxiety, depression, duration of illness, medications, history of trauma, family history of psychosis/schizophrenia and substance use/abuse;
- 3) Baseline neurocognitive variables (e.g. working memory, verbal memory, processing speed, sustained attention)

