4.2.2.3 Methodology – model development

The pool of potential prognostic factors for inclusion in our model will be based on the published systematic review [41], our own review undertaken in Phase I, and the output of the focus group work from Phase 1. All continuous covariates will be modelled as continuous covariates to avoid reducing the power to detect relationships and a loss of predictor information which can arise with categorisation. Linear and non-linear relationships will be considered including simple log transformations and more complex restricted cubic spline [66] and fractional polynomial options [67].

Given the difficulty of collecting certain information it is likely that some values may be missing for individuals which will cause a loss of power and precision. There is no established cut-off regarding an acceptable percentage of missing data. However, there is some evidence to suggest that that statistical analysis is likely to be biased when more than 10% of data are missing [68]. Therefore, in the case of more than 10% missing data for any covariate, multiple imputation will be used to impute missing values invoking Rubin's rule to combine estimates as necessary [69].

Logistic regression prognostic models should be built with a sample size of at least 10 events per variable (EPV) [64]. If our pool of prognostic factors together with relevant IPD from Phase 1 exceeds this sample size requirement, data reduction will be used [66]. In the first step variables with very narrow distributions will be removed. We will also consider whether it is sensible to remove variables with large amounts of missing data as it may be difficult to record these in practice. Backwards elimination according to Akaike's Information Criteria will then be used as an automatic selection procedure to determine variables in the final multivariable model [67].

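### The 10-events rule counts variables, yet splines and fractional polynomials are allowed, so it can be met with well under 10 events per estimated parameter

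*Protocol*

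**What the plan says.** Section 4.2.2.1 (Data) sets the minimum for developing the novel model at "at least 10 transition events per variable (EPV", and explains the consequence in terms of factors: "This may restrict the number of prognostic factors we can consider for inclusion in the model".

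Section 4.2.2.3 (model development) repeats the rule: "Logistic regression prognostic models should be built with a sample size of at least 10 events per variable (EPV". It ties data reduction to the same count: "If our pool of prognostic factors together with relevant IPD from Phase 1 exceeds this sample size requirement, data reduction will be used".

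The same section 4.2.2.3 says "All continuous covariates will be modelled as continuous covariates". It will consider linear and non-linear relationships, from simple log transformations to "more complex restricted cubic spline [66] and fractional polynomial options". It states no number of knots, no polynomial degree and no limit on degrees of freedom. Variables are then selected by backward elimination on AIC.

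Many of the candidates in section 4.1.1 are scores or scales, for example "Baseline neurocognitive variables (e.g. working memory, verbal memory, processing speed, sustained attention". Others, such as gender, ethnicity and family history, are binary or categorical.

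Section 4.2.2.4 plans 1000 bootstrap replications, a check on how consistently predictors and functional forms are chosen, possible revision of the model, and uniform shrinkage.

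**The concern.** Overfitting depends on how many parameters are estimated or tried, not on how many named factors they belong to. A rule that counts factors charges a 4-knot spline (three coefficients) the same as a straight line (one coefficient). A candidate list can then satisfy the rule, and so not trigger data reduction, while the ratio of events to parameters is a fraction of 10.

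This matters here because section 2 criticises earlier models for a low ratio of events to predictors and the overfitting that follows, and section 4.2.2 presents the novel model as free of those flaws. That model is also the fallback if updating existing models gives poor discrimination, so discrimination is the property that most needs protecting.

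**Working it through.** **Inputs from the protocol.** The threshold is 10 events per variable (4.2.2.1, 4.2.2.3). The functional forms are linear, log, restricted cubic spline and fractional polynomial (4.2.2.3). The 10 is an adopted rule and not the result of a calculation. The protocol gives no development event count, number of candidates or number of knots, so there is no figure to reproduce.

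**Step 1: events per parameter when the rule is just met.** With d coefficients per variable, events per parameter = 10 / d. A spline with k knots uses k − 1 coefficients. A second-degree fractional polynomial uses 2, or 4 if the two chosen powers are counted.

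| Form, used for every variable | d | Events per parameter |
|---|---|---|
| Linear or log | 1 | 10.0 |
| 3-knot spline | 2 | 5.0 |
| 4-knot spline | 3 | 3.3 |
| 5-knot spline | 4 | 2.5 |
| Fractional polynomial, degree 2 | 2 (4 with powers) | 5.0 (2.5) |

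**Step 2: mixed candidate lists.** If a share s of the variables is continuous with d coefficients each, and the rest use one each, events per parameter = 10 / (s·d + 1 − s).

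- s = 0.8: 10/1.8 = 5.6, 10/2.6 = 3.8 and 10/3.4 = 2.9, for d = 2, 3 and 4.
- s = 0.6: 10/1.6 = 6.25, 10/2.2 = 4.5 and 10/2.8 = 3.6.

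**Step 3: events needed.** For an assumed 10 continuous variables, the rule as written needs 10 × 10 = 100 events. At 10 events per parameter the need is 10 × 10 × d: 200, 300 or 400 for d = 2, 3 or 4.

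**Step 4: possible effect on performance, without selection (simulation, assumed inputs).** 150 data sets per model, 500 patients each, about 95 events, ten standard-normal predictors with truly linear effects, true c about 0.69. Performance was measured in 10,000 new patients before any shrinkage.

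| Terms | Parameters | Median calibration slope | Mean c |
|---|---|---|---|
| Linear | 10 | 0.76 | 0.676 |
| 3-knot spline | 20 | 0.59 | 0.659 |
| 4-knot spline | 30 | 0.48 | 0.647 |
| 5-knot spline | 40 | 0.39 | 0.635 |

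The loss in c with 4 knots is 0.676 − 0.647 = 0.029.

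**Step 5: adding the planned AIC elimination.** A second set of 150 data sets (500 patients, 20% events, true c 0.69, 4-knot splines, 20,000 new patients) gave these means:

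| Model | Slope | c |
|---|---|---|
| Linear, no selection | 0.78 | 0.671 |
| Splines, no selection | 0.48 | 0.641 |
| Linear, AIC | 0.79 | 0.668 |
| Splines, AIC drops whole variables only | 0.56 | 0.640 |
| Splines, AIC may also reduce a spline to linear | 0.64 | 0.654 |

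Against linear terms with AIC, the c loss is 0.668 − 0.640 = 0.028 for whole-variable elimination and 0.668 − 0.654 = 0.014 when splines may be simplified. A smaller set of 60 data sets with true c 0.68 put the latter at 0.640 − 0.628 = 0.012. Another repeat gave about 0.013, with spline slopes of 0.51 (whole variables) and 0.60 (simplified).

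**Step 6: what uniform shrinkage does.** It multiplies all coefficients by one positive constant. The order of patients by predicted risk does not change, so the c index does not change. Only the average slope is corrected.

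**The case against.** The strongest reply is that the protocol does not force splines on anything. Non-linear forms are only to be considered, linear and one-parameter log forms are on the same list, and AIC elimination follows. Section 4.2.2.4 then checks functional forms across bootstrap samples and allows revision where a form is not commonly chosen, which is the safeguard aimed at a curve fitted to noise. Ten is a floor, the pooled individual participant data may hold many more events, and several candidates are binary. The simulations make the truth linear, so splines can only lose; with real curvature they could gain. Knot numbers commonly belong in the statistical analysis plan.

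Much of this stands, and it limits the size of the point. It does not remove it. In the simulations AIC roughly halves the c loss at best, and leaves it whole if only entire variables are dropped. The bootstrap revision is conditional, has no stated criterion, and comes after the rule has admitted the terms. The absence of knot numbers is not the complaint: the protocol itself fixes the unit, the threshold and the trigger for data reduction, and an analysis plan that followed it would inherit them.

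A reader might infer three stronger things that the protocol does not support:

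- That the model will be built on about 3 events per parameter. That figure needs 4-knot splines on essentially all candidates and a rule that is only just met.
- That any lost discrimination is bound to pass unrepaired into validation. Section 4.2.2.4 provides for revision, and section 4.2.3 allows a promising existing model to be evaluated as well if the new one is unsatisfactory because of data limitations.
- That the Phase 3 cohort is the only external test. Section 4.2.2.1 also assesses discrimination and calibration in data from outside the UK.

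**Conclusion.** The point holds as a defect in how the rule is counted. As written, sections 4.2.2.1 and 4.2.2.3 can be satisfied at 2.5 to 5.0 events per parameter if every factor is continuous and modelled non-linearly, and at about 3.6 to 6.2 if 60% are continuous.

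The consequence is conditional. With 500 patients, 20% events, ten predictors, truly linear effects and 4-knot splines, all of them assumptions, the c index in new patients falls by about 0.03 with splines on every predictor or whole-variable elimination, and by about 0.013 if AIC may simplify splines. The calibration slope is about 0.5 to 0.6 after selection, against about 0.75 for unselected linear terms. Shrinkage can correct the slope but not the c index. The bootstrap check may reduce the loss by an amount that cannot be judged from the protocol. If the data hold far more than 10 events per factor, the effect is smaller. The change is worth making because it costs little.

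**What to change.** In sections 4.2.2.1 and 4.2.2.3, state the minimum as at least 10 events per candidate parameter. Count every spline term, fractional-polynomial term and category dummy considered before backward elimination, and say whether chosen polynomial powers are counted. Trigger data reduction when that total exceeds the number of events divided by 10. Once the candidate list and event count are known, and before modelling starts, allocate the available degrees of freedom across factors and allow non-linear terms only within that budget.

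The cost is a change of wording. The downside is fewer candidate factors or simpler functional forms, and so some risk of missing real curvature in factors that are not given extra degrees of freedom.

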4.2.2.2 Methodology – overall

In order to ensure transparency, we will develop and validate our model following the recommendations of the PROGRESS Group [65]. We will conform to the TRIPOD statement, a consensus-based guidance for improving the quality of reporting of multivariable prognostic model studies that includes 37 items covering 22 topics that should be included in any article describing the development or validation of a prognostic model[63].

There will be two stages to our prognostic modelling – model development, and internal validation (external validation of the novel model will take place in Phase 3 with a specifically-recruited UK-based cohort study).

4.2.2.3 Methodology – model development

The pool of potential prognostic factors for inclusion in our model will be based on the published systematic review [41], our own review undertaken in Phase I, and the output of the focus group work from Phase 1. All continuous covariates will be modelled as continuous covariates to avoid reducing the power to detect relationships and a loss of predictor information which can arise with categorisation. Linear and non-linear relationships will be considered including simple log transformations and more complex restricted cubic spline [66] and fractional polynomial options [67].

Given the difficulty of collecting certain information it is likely that some values may be missing for individuals which will cause a loss of power and precision. There is no established cut-off regarding an acceptable percentage of missing data. However, there is some evidence to suggest that that statistical analysis is likely to be biased when more than 10% of data are missing [68]. Therefore, in the case of more than 10% missing data for any covariate, multiple imputation will be used to impute missing values invoking Rubin's rule to combine estimates as necessary [69].

Logistic regression prognostic models should be built with a sample size of at least 10 events per variable (EPV) [64]. If our pool of prognostic factors together with relevant IPD from Phase 1 exceeds this sample size requirement, data reduction will be used [66]. In the first step variables with very narrow distributions will be removed. We will also consider whether it is sensible to remove variables with large amounts of missing data as it may be difficult to record these in practice. Backwards elimination according to Akaike's Information Criteria will then be used as an automatic selection procedure to determine variables in the final multivariable model [67].

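### The 10% per-covariate trigger for multiple imputation leaves the joint loss of records uncontrolled when every candidate predictor is at or below the limit

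*Protocol*

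**What the plan says.** Protocol section 4.2.2.3 covers development of a novel model, which section 4.2.2 reserves for the case where updating existing models is not enough. It accepts that "it is likely that some values may be missing for individuals which will cause a loss of power and precision". It then states that "There is no established cut-off regarding an acceptable percentage of missing data", cites evidence that "statistical analysis is likely to be biased when more than 10% of data are missing", and concludes that "in the case of more than 10% missing data for any covariate, multiple imputation will be used to impute missing values", with Rubin's rules used to combine estimates.

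Nothing is said about covariates with 10% or less missing, or about the share of records missing at least one covariate.

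Three other provisions bear on the point:

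- Sections 4.2.2.1 and 4.2.2.3 require at least 10 events per variable (EPV). Neither says whether events are counted before or after incomplete records drop out.
- Section 4.2.2.3 selects predictors by backwards elimination on Akaike's criterion, after data reduction that may remove variables with much missing data.
- Section 4.1.1 names about 22 factors for the data request: 5 socio-demographic, about 13 clinical (among them "general psychopathology, positive symptoms, negative symptoms, disorganisation, anxiety, depression, duration of illness, medications, history of trauma") and 4 neurocognitive.

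**The concern.** The reason and the rule are on different scales. The reason is about the share of the data that is missing; the rule looks at each covariate separately. A multivariable regression needs every covariate present for a person, so what matters is the share of people with any gap. Every covariate can satisfy the rule while that share is well above 10%. In that case no imputation is triggered, no other method is named, and software would by default fit the model to complete records only.

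Backwards elimination starts from the full candidate set, and comparisons by Akaike's criterion need a common set of records. The loss therefore depends on the whole candidate pool and not only on the predictors finally kept.

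What is at stake is precision and the number of transition events behind predictor selection. The protocol's own background (section 2) criticises earlier models for low EPV and poor reporting of missing data.

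**Working it through.** The protocol gives no number of records, events or complete cases for the development data, so there is no stated figure to reproduce.

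**Inputs.** From the protocol: the 10% trigger (section 4.2.2.3), the 10 EPV floor (sections 4.2.2.1 and 4.2.2.3) and about 22 named factors (section 4.1.1). Assumed: the number of candidates *k*, the missing fraction *m* of each, and how far the gaps overlap.

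**Formulae for the share of records lost without imputation.**

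- Gaps always in the same records: *m*
- Independent gaps: 1 − (1 − *m*)^*k*
- Gaps never in the same record: min(1, *k* × *m*)

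| *k*, *m* | Complete overlap | Independent | No overlap |
|---|---|---|---|
| 5 at 5% | 5% | 1 − 0.95^5 = 1 − 0.774 = 23% | 25% |
| 10 at 5% | 5% | 1 − 0.95^10 = 1 − 0.599 = 40% | 50% |
| 8 at 9% | 9% | 1 − 0.91^8 = 1 − 0.470 = 53% | 72% |

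**Partial overlap** (latent-normal model with equal correlation between gaps). Ten covariates at 5% lose 31% of records at correlation 0.3, 25% at 0.5 and 12% at 0.9. Ten covariates at the full 10% lose about 50%, 40% and 21% at the same correlations.

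**When half the records go.** With independent gaps, losing more than half takes 7 covariates at 10% (1 − 0.9^7 = 52%), 14 at 5% (51%), 23 at 3% (50.4%) or 35 at 2%.

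**Effect on EPV.** Suppose 10 EPV is just met before deletion and events are lost in proportion to records. The independent cases in the table then leave 10 × 0.774 = 7.7, 10 × 0.599 = 6.0 and 10 × 0.470 = 4.7 EPV. With complete overlap, 9.5, 9.5 and 9.1 remain.

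**The case against.** Several objections have weight.

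- **Complete-case analysis is inferred.** The protocol never names it, and an unseen statistical analysis plan may say more. That stands. The trigger itself is nevertheless a stated rule, and it gives no protection below the limit.
- **The trigger may apply to the whole dataset.** On this reading one covariate above 10% leads to imputation of all missing values, and the problem arises only when every candidate is at or below 10%. With about 22 factors drawn from several studies, that may be uncommon. The point made here is confined to that case, so it survives but is narrower.
- **The EPV rule may already protect the fit.** If events are counted on analysed records, the candidate list would shrink to suit, and data reduction could also help. The text does not say which count is meant. The floor also need not be breached: with an assumed 200 events and 8 candidates at 9%, 200 × 0.470 = 94 events remain, or 94 / 8 = 11.8 EPV.

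Two stronger readings are tempting and not supported. A reader might infer that estimates will be biased because missingness follows severity. Baseline severity is among the covariates, and missingness that depends on covariates alone does not bias a correctly specified complete-case logistic model. Dependence on outcome alone shifts mainly the intercept. Bias in the slopes needs something more, such as dependence on outcome and covariates jointly. A reader might also infer that the rule hides variables some studies never collected. The protocol does not say that the percentage is pooled; if it is, such a variable would usually exceed 10% and trigger imputation, unless the studies lacking it hold no more than a tenth of the records.

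**Conclusion.** The point holds as a weakness in a stated rule. When all candidates are at or below 10% missing, the per-covariate trigger permits a loss of records well above the 10% that the protocol treats as worrying: 23% to 53% in the three independent-gap cases, against 5% to 9% under complete overlap.

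The figures rest on assumed missing fractions, assumed overlap, an assumed number of candidates and complete-case fitting by default. It would be wrong to conclude that half the development data will be lost. That needs many covariates near the limit with largely independent gaps and none above it; fractions of 2% to 3%, or strong overlap, keep the loss below half for most plausible model sizes.

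The likely harm is lost precision and less stable predictor selection, with fewer events in the fit than the EPV count suggests. Bias is possible only under particular mechanisms. The change is worth making because it costs little and the threshold offers no clear gain.

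**What to change.** In section 4.2.2.3, delete the 10% per-covariate trigger. State that multiple imputation will be used whenever any candidate predictor is incomplete, with the outcome in the imputation model and clustering by study respected, and that complete-case analysis will be a sensitivity analysis. In sections 4.2.2.1 and 4.2.2.3, state that EPV is counted on the records actually analysed. Further detail of the imputation model can be left to the statistical analysis plan.

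Multiple imputation with Rubin's rules is already planned for the over-10% case, so the cost is a few sentences and computing time. No records are then lost to missing covariates, and the events counted towards EPV stay in the fit.
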